among young people. Preliminary evaluation data collected among an initial cohort of roughly 27,000 users has shown high levels of engagement in the program and high rates of abstinence among responders. Roughly ¾ of users set a quit date, with the most common quit date being the day of enrollment. Interactive keywords were used by 45.5% of teens and 38.4% of YA. Response rates to follow-up assessment questions were 36.9% at 14 days and 21.0% at 90 days. At 14 days, 60.8% of respondents indicated they had reduced or stopped using e-cigarettes altogether. At 90 days, 7-day point prevalence abstinence (ppa) was 25% and 30-day ppa was 16%. The high volume of enrollment in a short period of time, high levels of engagement with the program, and e-cigarette reduction and cessation results demonstrate that young people are interested in quitting vaping and can be engaged in an easily accessible, anonymous digital platform.

We recently completed an evaluation of This is Quitting with 2,588 young adults aged 18-24. Under an intention-to-treat analysis with missingness coded as vaping, abstinence rates were 24.1% among participants assigned to the intervention (This is Quitting) and 18.6% among participants in the assessment only control arm, a statistically significant difference (Odds Ratio=1.39, 95% CI 1.15-1.68, p< 0.001). [10]

Building on previous research, the primary aim of the current study is to conduct a comparative effectiveness trial to evaluate the effectiveness of *This is Quitting* in promoting abstinence from e-cigarettes among adolescents aged 13-17. This study is a 2-arm randomized controlled trial conducted among young users aged 13-17 recruited through online channels. Participants will be randomized to *This is Quitting* or an assessment-only control condition and followed for 7 months to roughly correspond to 6-months post-treatment. The secondary aim is to examine potential mediators of program effectiveness, including treatment engagement and changes in self-efficacy and perceived social support for quitting.

We will also include a waitlist control arm to evaluate the influence of assessment reactivity and retention incentives given relatively high quit rates among assessment-only control participants in the previous YA trial and the dearth of data on adolescent vaping cessation. This arm was not included in sample size calculations.

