The scientific, clinical, and public health communities are desperate for proven, evidence-based cessation resources to address the vaping epidemic among young people. We are uniquely positioned to address this urgent need given our extensive experience in conducting large-scale, rigorous research trials of digital tobacco cessation interventions and our expertise in working with young people. We plan to rapidly disseminate study results to benefit other researchers/service providers and use these results to further enhance the program.

METHODS

Subjects

We will randomize 1800 e-cigarette users aged 13-17 years old who are interested in quitting in the next 30 days to the two main intervention arms (900/arm). We will aim to randomize 450 to the waitlist control arm. Other eligibility criteria include past 30-day e-cigarette use and US residence. To fully enroll in the study, individuals must text a study-specific phone number and respond to the system-generated message.

Recruitment and Enrollment

Potential participants will respond to online ads on various social media platforms (Facebook, Instagram, etc.) if they are current e-cigarette users who are interested in quitting and willing to participate in a research study. Clicking on the ad will lead them to a webpage that provides details about what participation in the study entails and describes incentives for participation. Those who are interested will complete an eligibility screener followed by informed consent and a baseline assessment. Those who complete the baseline will be randomized into one of three arms (see below for additional details) and instructed to text a specific keyword corresponding to their treatment assignment to the same phone number. Only those who respond to the first message from the text message program within 24 hours will be fully enrolled into the study. This requirement will be made explicit.

Randomization

Randomization occurs after completion of the online enrollment process (completed baseline survey). A computer algorithm that is part of the survey software will automate random allocation.

Interventions

This is Quitting: Participants will be enrolled to receive messages from This is Quitting as described above.

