Assessment-only control: After an initial enrollment message, participants will be contacted monthly to assess e-cigarette use. At the end of the study, participants will receive information about how to sign up for This is Quitting if they are interested.

Waitlist control: After an initial enrollment message, participants will only be contacted at 1 and 7 months to complete the follow-up assessments; there will be no other contact via text message. At the end of the study, participants will receive information about how to sign up for This is Quitting if they are interested.

Potential Problems and Solutions

Loss to follow-up is the primary concern in trials involving digital interventions, especially ones that employ an assessment only or minimal contact controls. For the treatment and assessment only control arms, we expect at least 75% follow-up at 1-month and 65% at 7-months based on our previous and ongoing digital mobile-based evaluations. If follow-up rates are lower than expected early in the trial, we will consider shortening the 7-month follow-up to gather only abstinence outcomes.

To maximize follow up rates we will:

- 1) provide clear information about the study at the outset, including expectations for follow-up;
- 2) reimburse participants up to \$30 per follow-up assessment;
- 3) collect interim abstinence assessments via text ("Retention Messages": \$5 incentive for each response) for intervention and assessment-only control arms;
- 4) send reminders about follow-up surveys via email and text messages;
- 5) conduct phone follow-ups for those unreachable by email and text messages;
- 6) contact participants via social media private messaging function (if permission given); and,
- 7) emphasize the importance of survey completion regardless of abstinence status.

Conducting research online involving incentives carries the potential for fraud and participant deception as there are often no direct interactions with the participants.¹¹ To prevent fraudulent enrollments and participation from bots, we will utilize the following features on the Qualtrics survey platform:

- 1) Prevent multiple submission: Enabling this option allows Qualtrics to place a cookie on the browser the first time someone takes the survey. The user will be flagged as duplicate if they come back to take the survey from the same browser and device without having cleared their cookies.

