Outcome Measures. The primary outcome is self-reported 30-day point-prevalence abstinence (ppa) at 7-months but we will gather abstinence data at all follow-ups. Other quitting-related outcomes include change in motivation to quit, quit attempts, reduction in e-cigarette use, 7-day ppa, and continuous abstinence measured at each follow-up. Intervention satisfaction in both conditions will be measured with items about overall satisfaction and whether they would recommend it to a friend (scale from 0-10). Satisfaction with frequency of text messages will be measured.²⁸ To assess perceived message relevance, participants will be asked whether text messages "were written personally for you"²⁹ and "were directed at you personally".³⁰

Data Analysis Plan

[figure not shown]
Primary Analysis. Point-prevalence abstinence (ppa) at 7-months post-randomization will be compared across the treatment and control groups using logistic regression. All estimates will be adjusted for baseline confounders of the intervention-outcome relationship. We will identify potential moderators (e.g., age, gender, baseline motivation to quit) by analyzing interactions between treatment and selected variables. For

all moderators found to be associated with the primary outcome, we will examine the effects of treatment/moderator interaction terms on outcomes after entering main effects.

Secondary Analyses. Additional outcomes related to abstinence and treatment engagement will also be analyzed with logistic regression as secondary analyses. These include likelihood of making a quit attempt, likelihood of reducing e-cigarette use, and changes in confidence and self-efficacy in quitting e-cigarettes.

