Missing Data. Missing data will be handled in two ways. First, we will conduct an intent-to-treat (ITT) analysis in which participants who have been lost to follow up are assumed to be treatment failures (i.e., vaping). This analysis will be conducted because ITT analyses are common in the smoking cessation literature, despite simulations demonstrating that the approach is neither conservative nor anti-conservative but rather biased in favor of whichever condition contains less missingness. Second, we will supplement the ITT analyses with an analysis that uses a multiple imputation (MI) procedure to minimize bias in estimates and standard errors, under the assumption that outcomes are not missing at random (NMAR) but rather more likely to be missing for treatment failures (i.e., vaping) than treatment successes (i.e. abstinence). Since the magnitude of actual response bias is unknown, we will conduct a sensitivity analysis to evaluate the treatment effect on outcomes under a range of magnitudes, from equal odds of missing (OR=1) to five times more likely to be missing (OR=5).

Mediator Analysis. Our conceptual model is that treatment increases the odds of abstinence by increasing perceived social support and perceived self-efficacy for quitting. Those two constructs will be measured at baseline, 1-month and 7-months post-treatment. Change in those constructs from baseline will be evaluated with separate mediation analyses as presented in Figure 1. Specifically, we hypothesize that the effect of treatment on abstinence will be mediated by perceived social support and perceived self-efficacy, such that: (1) a significant effect A is found associating X with Z; (2) a significant effect B is found associating Z with Y; (3) a significant effect C is found associating X with Y; and (4) the effect of C is significantly attenuated when A and B are simultaneously included in the model.

PROTECTION OF HUMAN SUBJECTS

Human Subjects Involvement, Characteristics, and Design

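### Logistic regression is assigned to changes in confidence and self-efficacy with no cut-point or ordinal form; a binary split, if meant, would lose at least about 36% of the information

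*Combined protocol and SAP*

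**What the plan says.** Under Data Analysis Plan, Secondary Analyses, one method is named for the further outcomes: "Additional outcomes related to abstinence and treatment engagement will also be analyzed with logistic regression as secondary analyses". The next sentence lists them: "These include likelihood of making a quit attempt, likelihood of reducing e-cigarette use, and changes in confidence and self-efficacy in quitting e-cigarettes". The first two are the likelihood of an event, so logistic regression fits them. The last is a change in a construct.

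The Mediator Analysis paragraph treats self-efficacy, with social support, as a repeatedly measured construct: "Those two constructs will be measured at baseline, 1-month and 7-months post-treatment". It adds: "Change in those constructs from baseline will be evaluated with separate mediation analyses as presented in Figure 1". It does not name the model for the path from treatment to mediator.

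The protocol names no instrument, number of items, range or standard deviation for confidence or self-efficacy. It gives no cut-point, responder definition, ordinal model or linear model for the change. It does not say whether the baseline score enters the secondary models.

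**The concern.** A change from baseline on a multi-level score is not an outcome for ordinary (binary) logistic regression until someone cuts it. The Primary Analysis paragraph uses the same term, unqualified, for the yes/no abstinence outcome, so a binary model is the natural reading.

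Two things follow if that reading is right. First, the estimate and its p-value depend on where the change is cut, and nothing fixes the cut before the data are seen. Second, cutting a graded score discards information, so a real effect of the programme on self-efficacy is more likely to be missed. Self-efficacy is one of the two constructs through which the protocol expects the programme to work, so the result will be read with interest although it is secondary.

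**Working it through.** The plan states no power, effect size or standard deviation for these outcomes, so there is no figure of its own to reproduce.

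**Inputs from the protocol.** 900 per main arm (Subjects). Expected follow-up (Potential Problems and Solutions): "we expect at least 75% follow-up at 1-month and 65% at 7-months". Followed at 7 months: 0.65 × 900 = 585 per arm.

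**Assumptions, not in the protocol.** A roughly normal multi-level score with equal SD at baseline and follow-up; two-sided 5% test; treatment difference 0.15 SD; baseline to follow-up correlation r from 0.4 to 0.6.

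**1. Loss from the split alone.** For a small shift in a normal score, the efficiency of a binary split with proportion p on one side, relative to comparing means, is φ(z_p)² / [p(1 − p)].

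| Split | Calculation | Efficiency | Loss |
|---|---|---|---|
| 50/50 | 0.3989² / 0.25 | 0.637 | 36% |
| 70/30 | 0.3477² / 0.21 | 0.576 | 42% |
| 80/20 | 0.2800² / 0.16 | 0.490 | 51% |
| 90/10 | 0.1755² / 0.09 | 0.342 | 66% |

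The median split is the most favourable cut. It makes 585 per arm worth 585 × 0.637 ≈ 372. The loss from the split alone reaches one half only at about 79/21.

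**2. Further loss if the baseline score is left out.** The change score has variance 2(1 − r). The baseline-adjusted follow-up score has residual variance 1 − r². The ratio (1 − r²) / [2(1 − r)] = (1 + r)/2 is the efficiency of the unadjusted change score. Multiplying by the median-split factor 0.637:

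- r = 0.4: 0.70 × 0.637 = 0.446
- r = 0.5: 0.75 × 0.637 = 0.477
- r = 0.6: 0.80 × 0.637 = 0.509

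So about half is lost in total, but only when both losses apply.

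**3. Power at r = 0.5, 0.15 SD, 585 per arm.** √(585/2) = 17.10.

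- Baseline-adjusted linear model: 0.15 / √0.75 × 17.10 = 2.962; Φ(2.962 − 1.960) = 84.2%.
- Change score, unsplit: 0.15 / 1 × 17.10 = 2.565; Φ(0.605) = 72.7%.
- Change score split at the median, no baseline covariate: 2.565 × √0.637 = 2.047; Φ(0.087) = 53.5%.

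Over r = 0.4 to 0.6 the first ranges from 80% to 89% and the last from 46% to 63%.

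**4. Dependence on the effect size.** At r = 0.5 the comparison in step 3 (first against last line) becomes 98% against 78% at 0.20 SD and 99.9% against 93% at 0.25 SD. The gap narrows as the effect grows.

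**5. Binary model with the baseline score as covariate.** Simulating the r = 0.5 case of step 3 (median split of change; logistic model with treatment and baseline score) puts power at about 58% to 61%. This recovers part of the loss, but power stays well below 84%.

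**6. Ordinal logistic model.** With k equal-sized categories, scores s_i and dp_i = φ(c_{i−1}) − φ(c_i), where c_i are the category boundaries, efficiency is (Σ s_i dp_i)² / Var(s). For k = 3: the boundaries are ±0.431 and φ = 0.3636, so (0.3636 × 2/3)² / 0.0741 = 0.793. The same formula gives 0.888 for k = 5 and 0.935 for k = 10. The losses are about 21%, 11% and 6%.

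**The case against.** The strongest reply is that the plan is under-specified here and not committed to a poor method. Four parts of it carry weight.

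- **The term is not qualified as binary.** An ordinal logistic model needs no single cut-point and loses far less. A reader might infer that the plan forces a yes/no split. The text does not go that far, although using the same term for the binary primary outcome makes that reading the more likely one.
- **Leaving out the baseline score is not stated.** A reader might infer that the split by itself discards half the information. It does not: a median split costs 36%, and the rest comes from omitting the baseline score, on which the plan is silent. The Primary Analysis paragraph promises adjustment for baseline confounders; that may be meant to carry over, but it sits under the primary analysis and does not name the score.
- **The scale is unknown.** A multi-level, roughly normal score is inferred from the wording about change. The 0.15 SD difference has no source in the documents.
- **The mediation question has its own analysis.** A reader might infer that the test of the conceptual model is itself weakened. The Mediator Analysis paragraph names no logistic model or dichotomy, and Figure 1 is not shown, so the documents do not support that.

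What the reply leaves untouched is the mismatch: an outcome worded as a change sits under a method that needs categories, and no categories are given. Every binary version examined loses material power against the linear model, including the one that adjusts for baseline.

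**Conclusion.** The point holds, at minor severity. The method and the outcome do not match as written, and the missing cut-point leaves room for a choice made after the data are seen.

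The size is conditional. If a binary split is meant, the loss is at least about 36% under normality and grows as the split becomes uneven. If the baseline score is omitted as well, the total loss is about half for correlations of 0.4 to 0.6. The figures of 84% against about 54% power are one illustration, resting on an assumed 0.15 SD difference, r = 0.5 and 585 per arm. If an ordinal model is meant, the loss is small. The plan does not say which applies, so no single loss figure can be attributed to it. Only these secondary outcomes are affected; the primary abstinence outcome is truly binary.

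**What to change.** Keep logistic regression for making a quit attempt and for reducing use. For confidence and self-efficacy, state that the follow-up score will be analysed by linear regression on treatment, adjusted for the baseline score. If the measure is a single ordered item, state a proportional-odds model adjusted for the baseline response. Name the instrument and its range, so that the choice between the two can be checked. If the investigators do want a binary responder outcome, the cut-point should be fixed and justified before the data are examined.

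The cost is about one sentence of analysis-plan wording. Self-efficacy is already planned at baseline, 1 month and 7 months, so no new data and no change to the sample size are needed.

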Baseline Variables. To characterize the sample and explore potential moderators of treatment effectiveness, we will gather: additional demographics (student status, employment status); current ecigarette use and history (frequency and rate, 16,17 age of first use, motivation to quit and quitting history 18); nicotine dependence will be assessed with the Penn State Electronic Cigarette Dependence Index 19, EDS/PROMISE-E, 20 the Hooked on Nicotine Checklist, 21 and the E-cigarette Fagerström Test of Cigarette Dependence (e-FTCD) 22; other substance use (other tobacco products, alcohol) and mental health symptoms 23; and adverse childhood events. 24,25 For co-morbidities and adverse childhood events, we chose measures that are validated for use among adolescents. In order to minimize risk to participants, we deliberately avoided measures or deleted questions that assessed sensitive topics such as suicidality. Given evolving trends of e-cigarette use and perception, we will also ask about perception about harm from e-cigarettes, reasons for wanting to quit, and reasons for joining the study. To account for potential predictors of dropout, we will ask about motivation to use or quit e-cigarettes and potential barriers to quitting (e.g., social influences). We will assess baseline levels of perceived level of social support, 26,27 perceived social norms, and perceived self-efficacy for quitting and examine changes in these variables as potential mediators of treatment effectiveness.

Mediating Variables. We hypothesize that treatment engagement will mediate the relationship between treatment assignment and abstinence outcomes. We will extract data regarding replies to interactive text messages (e.g., setting a quit date, keyword use) as well as unsubscribe status, number of days enrolled, and total number of messages received. All text message interactions are date/time stamped.

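### Nothing keeps the lost-equals-vaping coding out of the engagement and mediation models, where it creates a spurious mediator-abstinence path if follow-up rises with the mediator

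*Combined protocol and SAP*

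**What the plan says.** Under Data Analysis Plan, Missing Data, the plan opens without limiting its scope: "Missing data will be handled in two ways". In the first way, "participants who have been lost to follow up are assumed to be treatment failures (i.e., vaping"). The second is an addition to the first: "we will supplement the ITT analyses with an analysis that uses a multiple imputation (MI) procedure to minimize bias in estimates and standard errors". That imputation assumes outcomes are missing not at random, and the odds of being missing for vaping versus abstinent participants are varied from 1 to 5. The purpose is stated narrowly: "we will conduct a sensitivity analysis to evaluate the treatment effect on outcomes under a range of magnitudes". The same paragraph admits that coding the lost as failures favours the condition with less missing data.

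The Mediator Analysis section comes next. It hypothesizes that "the effect of treatment on abstinence will be mediated by perceived social support and perceived self-efficacy" and sets four conditions: a significant path A (treatment to mediator), a significant path B (mediator to abstinence), a significant effect C (treatment to abstinence), and a significant attenuation of C. It does not say which version of the abstinence outcome is used or how missing mediator scores are handled.

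Under Measures, Mediating Variables, a further mediator is named: "We hypothesize that treatment engagement will mediate the relationship between treatment assignment and abstinence outcomes". It is taken from the message system: "We will extract data regarding replies to interactive text messages", along with unsubscribe status, days enrolled and messages received. Under Potential Problems and Solutions, for the two main arms, "we expect at least 75% follow-up at 1-month and 65% at 7-months".

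**The concern.** An analyst who follows the plan in order reaches path B with lost-equals-vaping as the first coding of the outcome. Coded abstinence is then true abstinence multiplied by response, so any variable that predicts response also appears to predict abstinence.

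The plan's caveat and sensitivity analysis deal with differences between randomized conditions. Mediators are not randomized, and the plan does not consider follow-up that differs by mediator level. The possibility is realistic. Engagement is measured partly by replies to texts, and text is also a reminder channel and the last route for collecting abstinence from non-responders. The baseline survey itself collects potential predictors of dropout.

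Exposure differs by mediator:

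- **Engagement** comes from logs and is known even for people who never answer a survey, so every lost outcome enters its model as vaping.
- **Self-efficacy and social support** are survey scores. The coding affects them only for people with a 1-month score and no 7-month outcome. A 7-month change score is usually missing together with the outcome.

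The secondary aim is at stake. If the program works and raises self-efficacy, A and C hold, and path B largely decides whether a mechanism is claimed.

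**Working it through.** **The plan's own figure.** The background section reports 24.1% versus 18.6% abstinent in the earlier young-adult trial (N = 2,588, missing coded as vaping), with odds ratio 1.39 (1.15-1.68). Arm sizes are not given, so equal arms of 1,294 are assumed.

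- OR = (0.241/0.759) / (0.186/0.814) = 1.390.
- SE of log OR = √[1/(1,294 × 0.241 × 0.759) + 1/(1,294 × 0.186 × 0.814)] = 0.097.
- 95% CI 1.150-1.679, p = 0.0007. The published figure is reproduced.

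The plan gives no figure for the engagement or mediation analyses.

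**Assumed inputs.** True abstinence is 24.1%/0.65 = 37.1%, unrelated to the mediator and equal in responders and non-responders. Mean 7-month follow-up is 65%. Two-sided alpha is 0.05 (the plan states none). The documents give no follow-up by mediator level, so the gaps are illustrative.

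**Engagement.** One arm of 900 is split into halves of 450 by engagement, with a true OR of 1. Coded abstinence = follow-up × 0.371.

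| Follow-up, high vs low | Coded abstinence | Spurious OR | False-positive rate |
|---|---|---|---|
| 65% vs 65% | 24.1% vs 24.1% | 1.00 | 5% |
| 70% vs 60% | 26.0% vs 22.3% | 1.23 | about 26% |
| 75% vs 55% | 27.8% vs 20.4% | 1.50 | about 74% |

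For the 20-point gap: (0.2782/0.7218) / (0.2041/0.7959) = 1.50. With true abstinence anywhere from 25% to 45%, the OR is 1.20-1.24 for a 10-point gap and 1.45-1.55 for a 20-point gap.

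**What imputation does to the 20-point case.** With the mediator in the model, set the odds of abstinence among the missing to the responders' odds divided by k, where k is the plan's missingness OR. The association is 1.00 at k = 1, 1.14 at k = 2 and 1.30 at k = 5, against 1.50 when all the missing are coded as vaping. Values above 1.00 are not artefacts if non-responders really do vape more to that degree. They show how far the answer depends on that assumption.

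**Self-efficacy at 1 month.** 1,800 × 0.75 = 1,350 people have a 1-month score. At the plan's follow-up figures, the share of them lacking a 7-month outcome can lie between (0.75 − 0.65)/0.75 = 13% and 0.35/0.75 = 47%. The simulation takes 20%. The mediator is normal with a 0.2 SD arm effect and no effect on abstinence. The odds of answering rise by a fixed factor per SD, and a logistic model of coded abstinence on arm and mediator is fitted.

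- Path B falsely significant: 4.9%, 22%, 48% and 89% for factors of 1.0, 1.3, 1.5 and 2.0. Responders-only stays at 4.7-5.1%.
- All four conditions met, no treatment effect on abstinence: 0.9%, 1.3% and 4.7% for factors of 1.3, 1.5 and 2.0. The plan names no test of attenuation, so a Sobel test is assumed.
- All four met, with a real direct effect (28.6% vs 37.1%, where 28.6% = 18.6%/0.65) and the real arm effect on the mediator: about 10%, 22% and 54%.
- All four met, with that effect on abstinence but no arm effect on the mediator: below 1%.

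Repeat runs of the four-condition rates differ by up to about five points.

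**The case against.** The strongest reply is that the plan never says the coding is used in these models. The Missing Data paragraph speaks of treatment failures, conditions and the treatment effect, which is the language of the randomized comparison. If its rule is general enough to reach the mediation models, so is its second part, the imputation. This stands in part. A reader might infer that the plan carries the coding into the mediator analyses and so builds in an association; the text supports only that nothing keeps it out. The imputation does not close the gap as written. It is supplementary, it is described for outcomes only, its sensitivity analysis is aimed at the treatment effect, and no imputation variables are listed.

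A second reply is that path B alone does not establish mediation. That is correct. A reader might take the 89% as the chance of reporting a false mechanism, but the four-condition rates are far lower unless the program truly affects both abstinence and the mediator.

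Third, the Mediator Analysis section models only social support and self-efficacy. Engagement is hypothesized as a mediator elsewhere, and no 450/450 split is planned, so the engagement table is an illustration. A 30-point gap would give an OR of 1.85 and about 98% rejection, but nothing in the documents supports a gap of that size.

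Fourth, the inputs are assumed. The 37.1% combines one trial's abstinence with another's expected follow-up and treats non-responders as quitting as often as responders, whereas the plan expects them to do worse. Follow-up also uses email, phone and payment, so answering the survey is not the same behaviour as replying to program texts. These points limit the size of the problem but do not remove the mechanism.

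**Conclusion.** The concern holds in conditional form. The plan leaves lost-equals-vaping as the default outcome coding for path B, recognises its bias only between conditions, and gives no rule for missing mediator scores. If follow-up rises with a mediator and some of those lost are abstinent, path B is inflated. If follow-up does not vary with the mediator, or all those lost are vaping, there is no bias from this source.

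Even a modest gap takes the path-B error rate well above 5%. The risk of a wrong overall mediation claim is small if the program has no effect on abstinence, and becomes material when the program works and also moves the mediator. All sizes rest on the assumed abstinence rate and follow-up gaps. It would also be wrong to read the expected 35% loss at 7 months as the share of miscoded outcomes in the self-efficacy model: people with no mediator score drop out of it unless imputed. The randomized comparison is not the subject of this point. The change should be made before analysis because it affects a stated aim and needs no new data.

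**What to change.** In the Missing Data and Mediator Analysis sections:

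- State that coding those lost as vaping applies to the randomized comparison of abstinence, and that the engagement and mediation analyses rest on the planned multiple imputation.
- List the imputation variables: arm, engagement, baseline and 1-month self-efficacy and social support, and the baseline predictors of dropout already collected.
- Impute missing mediator scores jointly with abstinence.
- Report path B and the mediation results over the same missingness OR range of 1 to 5, with responders-only as a check.
- Tabulate 7-month follow-up by level of each mediator, so that readers can see whether the condition for bias is present.

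The cost is SAP wording and extra analysis. Intervals for path B will be somewhat wider, and these secondary analyses will depart from the coding conventional in cessation trials.
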